### **AESIs**

Comprehensive assessment of any apparent toxicity experienced by each subject will be performed from the time of giving informed consent and throughout the study. The Investigator will report any AESI, whether observed by the Investigator or reported by the subject. The AESI reporting period for safety surveillance begins when the subject is initially included in the study (date of first signature of informed consent) and continues until last Safety Follow-up Visit defined as  $30 \pm 3$  days or  $90 \pm 6$  days (as a phone call) after the last dose of M4112, **CCI** or before start of any anticancer therapy, whatever comes first.

### **DLTs**

Each DLT has to be immediately recorded in the eCRF.

#### **7.4.1.5 Safety Reporting to Health Authorities, Independent Ethics Committees/Institutional Review Boards and Investigators**

The Sponsor will send appropriate safety notifications to Health Authorities in accordance with applicable laws and regulations.

The Investigator must comply with any applicable site-specific requirements related to the reporting of SAEs (particularly deaths) involving study subjects to the IEC/IRB that approved the study.

In accordance with ICH GCP, the Sponsor/designee will inform the Investigator of “findings that could adversely affect the safety of subjects, impact the conduct of the study or alter the IEC’s/IRB’s approval/favorable opinion to continue the study.” In particular and in line with

respective regulations, the Sponsor/designee will inform the Investigator of AEs that are both serious and unexpected and are considered to be related to the administered product (“suspected unexpected serious adverse reactions” or SUSARs). The Investigator should place copies of Safety Reports in the Investigator Site File. National regulations with regard to Safety Report notifications to Investigators will be taken into account.

When specifically required by regulations and guidelines, the Sponsor/designee will provide appropriate Safety Reports directly to the concerned lead IEC/IRB and will maintain records of these notifications. When direct reporting is not clearly defined by national or site-specific regulations, the Investigator will be responsible for promptly notifying the concerned IEC/IRB of any Safety Reports provided by the Sponsor/designee and of filing copies of all related correspondence in the Investigator Site File.

For studies covered by the European Directive 2001/20/EC, the Sponsor’s responsibilities regarding the reporting of SAEs/SUSARs/Safety Issues will be carried out in accordance with that Directive and with the related Detailed Guidance documents.

#### **7.4.1.6 Monitoring of Subjects with Adverse Events**

Any AE that occurs during the course of a clinical study must be monitored and followed up and are assessed for final outcome at the last Safety Follow-up Visit.

All SAEs ongoing at the Safety Follow-up Visits must be monitored and followed up by the Investigator until stabilization or until the outcome is known, unless the subject is documented as “lost to follow-up”. Reasonable attempts to obtain this information must be made and documented. It is also the responsibility of the Investigator to ensure that any necessary additional therapeutic measures and follow-up procedures are performed.

#### **Monitoring of Specific Adverse Events**

In addition to the standard AE and SAE monitoring, precautions to be taken in subjects exposed to CCI M4112 and management of specific AEs or ADRs are provided in Section 6.5.4 and Section 6.5.5.

#### **7.4.2 Pregnancy and In Utero Drug Exposure**

Only pregnancies considered by the Investigator to be related to study treatment (for example, resulting from a drug interaction with a contraceptive medication) are considered to be AEs. However, all pregnancies with an estimated conception date during the period defined in Section 7.4.1.3 must be recorded by convention in the AE page/section of the CRF. The same rule applies to pregnancies in female subjects and to pregnancies in female partners of male subjects. The Investigator must notify the Sponsor/designee in an expedited manner of any pregnancy using the paper Pregnancy Report Form, which must be transmitted according to the same timeline as described for SAE reporting in Section 7.4.1.5.

Investigators must actively follow up, document and report on the outcome of all these pregnancies, even if the subjects are withdrawn from the study.

The Investigator must notify the Sponsor/designee of these outcomes using the Pregnancy Report Form. If an abnormal outcome occurs, the SAE Report Form in the eCRF will be used if the subject sustains an event and the Parent-Child/Fetus Adverse Event Report Form if the child/fetus sustains an event.

Any abnormal outcome must be reported in an expedited manner as described in Section 7.4.1.5, while normal outcomes must be reported within 45 days after delivery.

In the event of a pregnancy in a subject occurring during the course of the study, the subject must be discontinued from study treatment immediately. The Sponsor/designee must be notified without delay and the subject must be followed as mentioned above.

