Subjects treated with M4112 should also be monitored for potential irAEs, which may first manifest after weeks of treatment. Such events may consist of persistent rash, diarrhea and colitis, autoimmune hepatitis, arthritis, glomerulonephritis, cardiomyopathy or uveitis and other inflammatory eye conditions. Risk management guidance is provided in Section 6.5.5.3.

No embryo-fetal toxicity study have been performed to date, therefore effects on pregnancy cannot be excluded, pregnancy and lactation are excluded from the study. Highly effective contraception must be used for men and women of childbearing potential (Section 5.3.1 and Section 5.3.2).

**Liver toxicity and irAEs will be considered AESIs for M4112 requiring expedited reporting from the Investigator to the Sponsor within 24 h of learning of its occurrence.**

CCI

CCI

CCI

Instructions for treatment interruption/discontinuation or modification of infusion-related reactions/hypersensitivity will be provided to investigators as well as guidance for medical management (Table 8).

CCI [REDACTED]. Inclusion criteria for the study will require adequate entry hemoglobin value. Respective hematological parameters will be monitored every week during the 1st cycle of dose escalation phase. Treatment modification, interruption, and discontinuation rules, depending on severity, will be provided. CCI [REDACTED]

CCI

CCI

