### **Follow-up Period**

The Safety Follow-up Visit is scheduled  $30 \pm 3$  days and  $90 \pm 6$  days (as a phone call) after the last dose of M4112, **CCI** or until resolution to Grade 1, before start of any new anticancer therapy, whatever comes first (see Section [5.5.1](#)).

Subjects who discontinue treatment must be followed on study until resolution of toxicity or until confirmed disease progression.

[figure not shown]

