### 5.3.1 Inclusion Criteria

For inclusion in the study, all of the following inclusion criteria must be fulfilled:

1. Signed written informed consent form (ICF) before any study-related procedure is undertaken that is not part of the standard subject management.
2. Male or female subjects  $\geq 18$  years of age.
3. Subject population

**In the dose escalation cohorts (Part IA [REDACTED]):** Histologically or cytologically proven advanced or metastatic solid malignancies for whom no effective standard therapy exists or has failed or subjects who are intolerant to established therapy known to provide clinical benefit for their condition

4. Eastern Cooperative Oncology Group Performance Status (ECOG PS) of 0 to 1 at Screening.
5. Subjects who have been treated previously with a checkpoint inhibitor may enroll.
6. Adequate hematological function as defined below:
  - a. Absolute neutrophil count  $\geq 1,500/\text{mm}^3$  or  $\geq 1.5 \times 10^9/\text{L}$
  - b. Platelet count  $\geq 100,000/\text{mm}^3$  or  $\geq 100 \times 10^9/\text{L}$
  - c. Hemoglobin  $\geq 9 \text{ g/dL}$ .
7. Adequate hepatic function defined: by a total bilirubin level  $\leq 1.5 \times$  upper limit of normal (ULN), an AST level  $\leq 2.5 \times$  ULN, and an ALT level  $\leq 2.5 \times$  ULN

- a. Subjects with documented Gilbert disease are allowed if total bilirubin  $> 1.5 \times \text{ULN}$  but  $< 3 \times \text{ULN}$
- b. Subjects with tumor involvement in their liver:  $\text{AST} < 3.0 \times \text{ULN}$ ,  $\text{ALT} < 3.0 \times \text{ULN}$ , with normal bilirubin  $\leq 1.5 \times \text{ULN}$  and  $\text{INR} < 1.5$ .

8. Adequate renal function defined by an estimated glomerular filtration rate  $> 50 \text{ mL/min}$  according to the Cockcroft-Gault formula or normal creatinine laboratory values

(Glomerular filtration rate [ $\text{mL/min}/1.73 \text{ m}^2$ ] =  $175 \times \text{serum creatinine } (\text{S}_{\text{cr}})^{-1.154} \times \text{age} - 0.203 \times 1.212$  [if African American]  $\times 0.742$  [if female])

9. Male participants must agree to use and to have their female partners use a highly effective contraception (i.e., methods with a failure rate of less than 1 % per year) as detailed in [Appendix I](#) of this protocol 30 days before first dose of study treatment (as appropriate), during the treatment period and for at least 60 days after the last dose of study treatment of M4112 as single agent **CCI**  

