#### **7.4.1.3 Definition of the Adverse Event Reporting Period**

The AE reporting period for safety surveillance begins when the subject is initially included in the study (date of first signature of informed consent) and continues through the  $30 \pm 3$  days Safety Follow-up Visit or  $90 \pm 6$  days Safety Follow-up Visit (for Part IB and Part IC; as a phone call). After the Safety Follow-up Visit all SAEs and treatment-related nonserious AEs need to be documented up until stabilization or until the outcome is known, unless the subject is documented as "lost to follow-up".

Any SAE assessed as related to IMP must be reported whenever it occurs, irrespective of the time elapsed since the last administration of IMP.

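### In Part IA the explicit pregnancy-recording window closes 27 to 33 days before the required post-dose contraception period ends, and no other rule clearly covers the gap

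*Protocol*

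**What the plan says.** **Recording rule.** Protocol Section 7.4.2 states that "all pregnancies with an estimated conception date during the period defined in Section 7.4.1.3 must be recorded by convention" in the AE section of the case report form. It applies the same rule to female subjects and to female partners of male subjects. It then requires expedited notification of any pregnancy on a dedicated form, and follow-up of the outcome of the pregnancies just referred to.

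**Period it points to.** Section 7.4.1.3: "The AE reporting period for safety surveillance begins when the subject is initially included in the study", meaning at first consent, and it "continues through the $30 \pm 3$ days Safety Follow-up Visit". The alternative end, at 90 ± 6 days, is tied to the "Safety Follow-up Visit (for Part IB and Part IC; as a phone call". Table 1, the schedule for Part IA, has a single safety follow-up column, at 30 ± 3 days. The synopsis also limits the 90-day contact to Parts IB and IC.

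**Contraception period.** Inclusion criteria 9 (men) and 10b (women of childbearing potential) in Section 5.3.1 require highly effective contraception "during the treatment period and for at least 60 days after the last dose of study treatment of M4112 as single agent". Note b on hormonal methods in Appendix I uses the same 60 days.

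**Reason for caution.** The risk discussion in Section 3.4.2.1 says: "No embryo-fetal toxicity study have been performed to date, therefore effects on pregnancy cannot be excluded".

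**Conflicting follow-up text.** Section 5.1 sets the later contact at 90 ± 6 "days (as a phone call) after the last dose of M4112" without restricting it to any study part.

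**The concern.** The protocol asks subjects to prevent conception for at least 60 days after the last single-agent dose, but its explicit recording rule stops at about day 30. A conception on day 45, in a subject or in a male subject's partner, falls inside the first period and outside the second. A site that follows 7.4.2 literally has no clear duty to enter it in the case report form or to follow it to outcome.

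This is a first-in-human study with no embryo-fetal study behind it. Inclusion criterion 10 adds that the effect of M4112 on CYP3A4, and so on some hormonal contraceptives, is unknown. A reported pregnancy would be one of the few sources of human information on exposure around conception. No endpoint, escalation decision or planned analysis depends on the rule. What is at stake is whether a rare safety report is captured.

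**Working it through.** The plan gives no figure to reproduce. The check compares two windows and then scales the gap.

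**Inputs**
- End of pregnancy recording in Part IA: 30 ± 3 days after the last dose, so day 27, 30 or 33 (Sections 7.4.2 and 7.4.1.3, Table 1).
- End of required contraception: day 60 at the earliest (Section 5.3.1, criteria 9 and 10b; Appendix I).
- Failure rate of a highly effective method: below 1% per year (Section 5.3.1).
- Monotherapy subjects: approximately 24 (synopsis), or 24 to 30 evaluable (Section 8.1).
- Treatment duration: not given. Assumed range 28 to 336 days.

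**Step 1. Gap after the last dose** = 60 − visit day
- Visit on day 33: 60 − 33 = 27 days; 27/60 = 45%
- Visit on day 30: 60 − 30 = 30 days; 30/60 = 50%
- Visit on day 27: 60 − 27 = 33 days; 33/60 = 55%

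Sixty days is a minimum, so these gaps are minimums too.

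**Step 2. Gap as a share of treatment plus 60 days** = 30/(60 + T), with the visit on day 30
- T = 28: 30/88 = 34% (27/88 = 31% to 33/88 = 38% across the visit window)
- T = 84: 30/144 = 21%
- T = 336: 30/396 = 8%

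**Step 3. Expected conceptions in the gap**, taking the failure rate at its 1% ceiling and every subject as at risk
- 24 × 0.01 × 30/365.25 = 0.020
- 30 × 0.01 × 33/365.25 = 0.027

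**Step 4. Does another rule close the gap?**
- *Pregnancy tests:* the last scheduled test is at the 30 ± 3 day visit (Section 7.4.4).
- *Later contact:* subjects who stop without progression are not followed after the safety visits (Section 7.1.3).
- *Late discovery:* a conception dated before the 30-day visit but found later is covered, because the rule uses conception date. The gap concerns later conceptions only.
- *Notification:* the any-pregnancy sentence in 7.4.2 carries no date limit of its own, but it follows directly on the sentences that set the date limit. It can be read either way.
- *SAE route:* Section 7.4.1.3 requires related SAEs to be reported at any time. Under 7.4.2 a pregnancy is an AE only if judged treatment-related, so an unrelated conception on day 45 does not trigger this.

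**Step 5. Parts IB and IC.** The 90 ± 6 day period ends between day 84 and day 96, so measured against 60 days there is no gap. The contraception period for those parts is redacted, so no conclusion is drawn. Sections 4 and 7 of the analysis plan state that the study ended before they opened.

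**The case against.** The strongest reply is that 7.4.2 ties only the case report form entry to the AE reporting period. Expedited notification is required for any pregnancy, and the outcome duty follows that sentence, so it could extend to any pregnancy as well. A congenital anomaly is an SAE under Section 7.4.1.1, and if assessed as related it is reportable without time limit. This stands in part. A reader might infer that conceptions after day 30 would never be reported or followed, and the text does not support that. It supports less: recording is bounded, and the scope of notification and outcome follow-up is open to two readings.

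A reader might also take 45% to 55% as the share of at-risk conceptions missed. It is a share of post-dose days only. Treatment time also lies within the contraception period, the documents contain no conception data, and Step 2 shows how quickly the share falls.

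A third reply is that Section 5.1 provides a 90-day call for everyone. But the synopsis, Section 7.4.1.3 and Table 1 do not give it to Part IA, so this is a further inconsistency and does not rescue the rule. Finally, the protocol calls the 60 days a contraception requirement and does not define it as an exposure window. That is correct, and much of the supporting nonclinical text is redacted. The point rests only on the two periods not matching.

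**Conclusion.** The mismatch holds for Part IA. Explicit pregnancy recording ends at day 27 to 33 after the last dose, while contraception is required to at least day 60. That leaves 27 to 33 days in which a conception is not clearly required to be recorded or followed to outcome. The gap is 45% to 55% of the 60 post-dose days, and about 34% or less of the whole treatment-plus-60-day period once one cycle has been given. The latter figure rests on assumed treatment durations.

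The practical yield is very small: about 0.02 to 0.03 expected conceptions, even on the generous assumption that every subject is at risk at the 1% ceiling. The case for changing the text is that the rule is a safety-reporting duty in a first-in-human study without embryo-fetal data, and that correcting it costs almost nothing.

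**What to change.** In Section 7.4.2, keep the start at informed consent and extend only the end. Recording, notification and outcome follow-up should apply to conceptions from consent until the later of two dates: the end of the Section 7.4.1.3 period, and the end of the contraception period in criteria 9 and 10 (at least 60 days after the last single-agent dose). State that this covers female subjects and female partners of male subjects, and that all three duties share the same window, which removes the ambiguity about notification.

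The start should not move to first dose. That would drop conceptions during screening, up to 28 days, which the present rule covers.

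At the 30-day visit, tell subjects to report any conception up to the new end date, and put this in the consent and site instructions. Separately, reconcile the unrestricted 90 ± 6 day call in Section 5.1 with the synopsis and Section 7.4.1.3, which limit it to Parts IB and IC.

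The cost is a short text change, with no added visit or test, and an occasional extra pregnancy report after the last visit.

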### **7.4.3 Clinical Laboratory Safety Assessments**

Blood and urine samples will be collected for the following clinical laboratory safety tests (Table 10), following the timing noted in the Schedule of Assessments (Table 1, Table 2, and Table 3). All samples should be clearly identified.

The Sponsor should receive a list of laboratory reference ranges before shipment of study drug. Any change in laboratory normal ranges during the study should be forwarded to Sponsor.

All clinical laboratory samples for the assessment of the relevant safety parameters, will be collected and analyzed locally. Local laboratory samples and results will be recorded in the eCRFs according to the eCRF completion guidelines. The report of the results must be retained as a part of the subject's medical record or source documents. Blood samples for the full safety tests will be taken from fasted subjects. If confirmation of a subject's postmenopausal status is necessary, an FSH level will also be performed at Screening.

**Table 10 Clinical Laboratory Safety Assessments**

Serum Chemistry	Hematology	Coagulation
Albumin	Absolute lymphocyte count	Activated partial thromboplastin time
Alkaline phosphatase a	Absolute neutrophil count	Prothrombin time/International normalized ratio (Quick, INR)
Alanine aminotransferase a	Hematocrit	
Amylase	Hemoglobin	
Aspartate aminotransferase a	Platelet count	Basic Urinalysis (dipstick, including macroscopic appearance, bilirubin, blood, color, glucose, ketones, leukocyte esterase, nitrite, pH, protein, specific gravity, urobilinogen)
Gamma glutamyltransferase	Red blood cell count	
Blood urea nitrogen/total urea a	White blood cell count and differential count	Full urinalysis (dipstick plus microscopic evaluation) to be performed only at the Screening and End of Treatment Visit.
Calcium a	Red blood cell morphology	
Chloride a	Reticulocytes	
Creatine kinase	Mean corpuscular hemoglobin	
Creatinine a	Mean corpuscular volume	Hormones
C-reactive protein	Mean corpuscular hemoglobin concentration	Follicle-stimulating hormone (if applicable) Serum/urine $\beta$ -human chorionic gonadotropin (if applicable)
Glucose a		T4 and TSH
Lactate dehydrogenase		
Lipase		
Phosphorus/phosphates a		
Magnesium a		
Potassium a		
Sodium a	Serology	
Total bilirubin/indirect bilirubin a	HBsAg, HBcAb	
Total protein	HBV DNA (quantitative PCR)	
Troponin-T	HCVAb, HCV RNA (quantitative PCR)	
Uric acid		

HBcAb = Hepatitis B core antibody; HBsAg = hepatitis B surface antigen; HBV = hepatitis B virus; HCV = hepatitis C virus; HCVAb = hepatitis C virus antibody; T4 = thyroxine; TSH = thyroid-stimulating hormone.

a Core serum chemistries. Blood samples for serum chemistry profile will be obtained prior to the administration of the study drugs. Full serum chemistry will be performed at Screening and in Cycle 1 on Day 1 and Day 15; core chemistry in Cycle 1 on Day 8 and Day 22. In Cycle 2 to 6 thereafter, full chemistry will be performed on Day 1 and core chemistry on Day 15. From Cycle 7 onwards, full chemistry will be performed on Day 1 of every cycle and at the End of Treatment and Safety Follow-up Visits

If a subject has a clinically significant abnormal laboratory test value that is not present at Baseline, the test will be repeated weekly and the subject will be followed until the test value has returned to the normal range or the Investigator has determined that the abnormality is chronic or stable.

#### 7.4.4 Vital Signs, Physical Examinations, and Other Assessments

Vital signs, (blood pressure, pulse, respiratory rate, temperature,) should be assessed predose (within 15 min of oral dosing and infusion), and then every 15 min [REDACTED] [REDACTED], during infusion and for an additional 2 h post-infusion. If vital signs are not stable after 2 h (either blood pressure  $> 140/ > 90$  mmHg or  $< 90/ < 60$  mmHg compared to normal blood pressure at start or changes of  $> 20$  reading points between measurements, for heart rate and respiration rate changes of  $\geq 20\%$  compared to start) then continue monitoring every 15 min until stable on 2 consecutive repeated measurements. Consider hospital observation for prolonged vital sign changes or instability. As a routine precaution, subjects enrolled in this study must be observed for at least 8 h after infusion during Day 1 and Day 15 (continue vital signs every 60 min) of Cycle 1 and 2 h post infusion in follow-on cycles, in an area with resuscitation equipment and emergency agents (see [Table 1](#), [Table 2](#), [Table 3](#)).

ECOG PS, and 12-lead ECG (see Section [7.2.6](#) for 12-lead ECG details) will be assessed at time points indicated in the Schedule of Assessments ([Table 1](#), [Table 2](#), and [Table 3](#)).

A physical examination will be conducted at Screening and at subsequent visits as indicated in the Schedules of Assessments ([Table 1](#), [Table 2](#), and [Table 3](#)) and documented in the eCRF. Abnormal findings are to be reassessed at subsequent visits.

Body weight will be recorded at Screening and at subsequent visits as indicated in the Schedules of Assessments ([Table 1](#), [Table 2](#), and [Table 3](#)) and documented in the eCRF. Height will be measured at Screening only.

All newly diagnosed or worsening conditions, signs, and symptoms observed from screening, whether related to study treatment or not, are to be reported as AEs.

For female subjects of childbearing potential, a serum  $\beta$ HCG pregnancy test will be carried out during the Screening phase and a urine  $\beta$ HCG pregnancy test at the subsequent visits and at the Safety Follow-up visit of  $30 \pm 3$  days as indicated in the Schedules of Assessments ([Table 1](#), [Table 2](#), and [Table 3](#)). Results of the most recent pregnancy test (within the last 28 days) should be available prior to the next dosing of the study treatment. Subjects who are postmenopausal (age-related amenorrhea  $\geq 12$  consecutive months or FSH  $> 40$  mIU/mL), or who had undergone hysterectomy or bilateral oophorectomy are exempt from pregnancy testing.

Total volume of blood to be collected per subject will be approximately 20 mL for Screening and approximately 220 to 250 mL per cycle.

